9.3.3 Adverse Events of Special Interest

An Adverse Event of Special Interest (AESI) is an AE designated by Guerbet for transmission to Pharmacovigilance in the same time frame as an SAE.

The list of AESI for this protocol is the following:

- Nephrogenic Systemic Fibrosis (NSF).
- Torsade de pointes
- Sudden death;
- Ventricular tachycardia;
- Ventricular fibrillation and flutter;
- Syncope (excluding vasovagal reaction due to blood sampling);
- Seizures

Also, any suspicion of transmission of an infectious agent via an IMP/AMP should be considered as a serious and processed as an SAE.

In addition, any adverse event resulting from an occupational exposure may be directly reported to Guerbet.

9.3.4 Any suspicion of transmission of an infectious agent via an IMP or moxifloxacin

Any suspicion of transmission of an infectious agent via an IMP or moxifloxacin should be considered as serious and processed as an SAE.

9.4 Other important safety issue /New fact

Any safety issues that may alter the current benefit-risk assessment of an investigational medicinal product, or would be sufficient to consider changes in the trial drug administration or would involve any update of trial documents or in the overall conduct of the trial, should be evaluated by the sponsor. It includes any new event likely to affect the safety of the subjects and that may be related to the conduct of the trial or the development of the trial drug such as:

- A SAE which could lead to the modification of the conduct of the trial
- A significant hazard to the subject population such as lack of efficacy of an IMP used for the treatment of a life-threatening disease (if applicable).
- A new major finding from an animal trial,
- A temporary halt of a trial for safety reasons if the trial is conducted with the same investigational medicinal products in another country by the same sponsor,
- Recommendations of the DMC, if any, where relevant for the safety of subjects,
- Any serious adverse reaction, expected or not, involving healthy volunteers.

According to local requirements, Guerbet or its representatives will communicate relevant safety information to the appropriate agency (ies), IEC/IRB and/or all active investigators, as it becomes available.

Consequently, this type of important safety issue might lead also to:

- Urgent safety measures and their notification
- Substantial amendments
- Premature discontinuation of the trial
- Premature discontinuation of the subject

9.5 Unblinding Procedures

The blinding system will be made of two sets of envelopes.

One sealed envelopes set is kept at the phase I clinical trial unit, the other at Guerbet pharmacovigilance representatives (Sérénité 24/24h) .The sets of envelopes should be kept in a safe place and accessible to any person authorized to unblind.

The investigator may, under exceptional circumstances unblind the individual trial treatment group (sequence) if he/she considers that this procedure is relevant to the safety of the trial subject. Individual trial treatment unblinding is described in [section 5.3.4](#). Unblinding must be documented on the opened envelope, in the subject medical file, completed in the SAE form sent to Guerbet Pharmacovigilance Department, if applicable.

Suspected Unexpected Serious Adverse Reaction (SUSARs) will be unblinded by Guerbet Pharmacovigilance Department for regulatory reporting purposes; however, these SUSARs will remain blinded to the investigator and to Guerbet personnel responsible for trial management, data analysis, and interpretation of results at the trial's conclusion.

10 PREMATURE DISCONTINUATION OF THE TRIAL

10.1 Premature Discontinuation of the Trial per Guerbet Decision

Guerbet reserves the right to discontinue the trial at any time for medical, administrative or other reasons.

Guerbet will inform the relevant authorities in each country, the ethics committees, the trial site investigators, pharmacists and hospital authorities according to the regulatory texts in force.

10.2 Reasons for Subject's premature discontinuation

Screening Failure: a subject may be discontinued from trial in case of non-fulfillment of eligibility criteria. Subject having been screened and meeting all selection criteria but not included in the 28 days screening period could be re-screened. This implies that the subject will sign a new informed consent form before performing the screening visit and will be allocated with a new trial subject number.

Criteria for premature discontinuation of subjects:

- Adverse Event (according to the investigator's judgement);
- Withdrawal of subject's consent;
- Subject lost to follow-up (date of last contact will be documented in the medical file and the eCRF). Any effort will be undertaken to know the reason for this loss to follow-up and/or to exclude any adverse reaction as this reason. This will be documented in the medical file;
- Discovery of an unexpected, significant, or unacceptable risk to the subjects enrolled in the trial;
- At the discretion of the investigator if the subject safety or well-being is not compatible with trial continuation;

Specific subjects stopping rules:

If any of the events described below occurs, injection of IMP/AMP should not be done and the subject should be discontinued from the trial:

- Torsade de pointes event;
- Ventricular tachycardia;
- Ventricular fibrillation and flutter;
- Seizures;
- QTc Fridericia >500 ms or an increase of > 60 ms (ECG Core laboratory data) over the baseline (the baseline for safety ECG is defined as the 12-leads triplicate ECGs recorded within 1 hour prior to each administration) measurement before each IMP/AMP administration;
- Renal toxicity characterized by an increase in serum creatinine by more than 25% or 0.5 mg/dl (44 µmol/l) compared to the baseline value;
- Any events which investigator or Guerbet considers raising a significant concern.

Specific trial stopping rules:

If this event described below occurs, enrolment should be suspended and the trial will be on hold:

- Torsade de pointes event in 1 subject;
- Sudden death in 1 subject;
- Ventricular tachycardia in 2 subjects;
- Ventricular fibrillation and flutter in 2 subjects;
- Seizures in 2 subjects;
- QTc Fridericia >500 ms or an increase of > 60 ms (ECG Core laboratory data) over the baseline (the baseline for safety ECG is defined as the 12-leads triplicate ECGs recorded within 1 hour prior to each administration) repeated in 2 subjects;
- Renal toxicity characterized by an increase in serum creatinine by more than 25% or 0.5 mg/dl (44 µmol/l) compared to the baseline value repeated in 2 subjects;

The DMC will review the cases and will decide to stop definitely the trial or not.

Data collected for subjects subsequently discontinuing from the trial (please refer to [section 14.3.2](#)):

For subjects prematurely discontinuing the trial, all data available at the time of discontinuation will be reported in the medical file and the eCRF (e.g.: inclusion data, safety data, administration data, P03277 plasma concentration data, ECG data and reason for discontinuation). The investigator must make every effort to collect and record all follow-up safety information (i.e., adverse events, injection-site tolerance, as appropriate), unless the subject withdraws consent for further data collection/participation for/in the trial.

11 STATISTICAL ANALYSIS

The following section summarizes the statistical analysis method, which is fully described in the Statistical Analysis Plan.

Continuous variables (e.g., age) will be summarized using the number of observations (n), mean, standard deviation (SD), median, minimum, and maximum.

Categorical variables (e.g., sex, race and ethnicity) will be summarized using the number of observations (n) and percentage in each category.

11.1 Statistical Method (null and alternative hypotheses)

Primary analysis

Primary endpoint is defined as the largest time-matched placebo-corrected, change-from-baseline mean effect of the two P03277 doses of QT interval expressed as QTc according to Fridericia's formula ($\Delta\Delta\text{QTcF}$) (in ms).

Primary endpoint is considered as following a standard normal distribution. Normality will be checked by means of plots.

Per ICH E14, a "negative" (successful) 'thorough QT/QTc trial' is one in which the upper bound of the 95% one-sided confidence interval for the largest time-matched placebo-corrected, change-from-baseline mean effect of the drug on the QTc interval excludes 10 ms. Consequently, the trial must show that both 0.1 and 0.3 mmol/kg doses of P03277 do not increase the QT interval corrected by Fridericia formula (QTcF) at all timepoints.

The null hypothesis is that the difference between each of the two doses of P03277 and placebo for the largest mean change from baseline for the QTcF is greater than the non-inferiority margin set to 10 ms according to regulatory guidance. An Intersection-Union test is performed at a one-sided 5% significance level. This is equivalent to compare at each timepoint the upper limit of the two-sided 90% confidence intervals of the difference between each of the two doses of P03277 and placebo with the non-inferiority margin of 10 ms. To conclude that P03277 is non-inferior to placebo, the null hypothesis has to be rejected for all timepoints and both doses simultaneously hence the overall Type I error rate does not need to be adjusted.

Assay sensitivity

Assay sensitivity assessment is defined as the largest time-matched placebo-corrected, change-from-baseline mean effect of moxifloxacin of QT interval expressed as QTc according to Fridericia's formula ($\Delta\Delta\text{QTcF}$)(in ms).

In order to validate the assay sensitivity of the trial, the trial must show that the positive control increase the QTcF by at least 5 ms for at least one timepoint.

The null hypothesis is that the difference between the positive control and placebo for the mean change from baseline for the QTcF is less than 5 ms according to regulatory guidance. This test is performed one-sided at the 5% significance level which is equivalent to compare the upper limit of the two-sided 90% confidence intervals of the difference with 5 ms. To conclude that positive control is superior to placebo, the null hypothesis has to be rejected at, at least, one timepoint.

As multiple timepoints are examined separately, the overall Type I error rate needs to be adjusted. To address this issue, the method described by Hochberg and Tamhane will be used. To minimize the correction and because the positive control effect is well known, only five timepoint around the peak effect (1h, 1h30, 2h, 3h and 4h) will be used.

11.2 Sample Size

A total of 48 subjects will be included in the study trial.

The sample size is determined using published recommendations for a thorough QT trial (Statistical Issues Including Design and Sample Size Calculation in Thorough QT/QTc Studies [4]).

N can be estimated by $N = 2 * (t_{\alpha}(\gamma) + t_{\beta}(\gamma))^2 [\sigma / (\delta - 10)]^2$

where

- σ^2 is the within subject variability
- $\gamma = N - 2$
- $\beta' = 1 - (1 - \beta)^{1/L}$ where β is the Type II error and L the number of measurements
- α is the Type I error
- $t_{\alpha}(\gamma)$ the critical values for a Student T distribution with γ degrees of freedom at an α level.
- δ is the expected difference between active drug and placebo (0 if no difference expected, >0 if drug is expected to slightly increase QT)

Considering an expected intra-variability of the primary endpoint of $\sigma = 9$ ms and an expected difference of $\delta = 2$ ms between P03277 (two doses) and placebo, 40 subjects are needed to demonstrate non-inferiority with a non-inferiority margin of 10 ms, a power of $1 - \beta = 85\%$ and a Type I error of $\alpha = 5\%$ one-sided on the $L = 9$ measurements.

This sample size is also sufficient to detect a difference of 5 ms (with an expected difference of 12 ms for at least one timepoint and an expected intra-variability of the primary endpoint of $\sigma = 9$ ms) of the primary endpoint between moxifloxacin and placebo with a power of 85%.

To account for potential dropouts and/or unevaluable data points, 48 subjects will be randomized in the trial. The recruitment could be stopped before 48 subjects from the time the number of fully evaluable subjects for the primary criterion is 40. That is to say having took part to the study, till the last scheduled ECG Holter recording.

A dropout is a subject who is prematurely discontinuing the trial before the end of the last Holter ECG recording.

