11.3.2 Data Sets Analyzed

There will be four subject sets defined for this trial: All enrolled subjects set, the Safety Set (SS), the Full Analysis Set (FAS) and the Per-Protocol Set (PPS).

All enrolled Subjects Set will include all subjects having signed their inform consent form. This set will be used for subject disposition summaries and individual listings.

The Safety Set will include all subjects, receiving at least one administration of IMP/AMP, regardless of the quantity. This set will be used for evaluation of safety and description of demographic data and baseline characteristics.

The Full Analysis Set will include all randomized subjects. This set will be used for evaluation of cardiac safety and description of demographic data and baseline characteristics.

The Per Protocol Set will be a subset of the FAS and will include all subjects who have no major protocol deviations throughout their whole trial period. Major deviations will be defined as having an impact on the primary criterion. Primary analysis will be performed on this set.

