### 3.3. Determination of sample size

A total of 48 subjects will be included in the study trial.

The sample size is determined using published recommendations for a thorough QT trial [4].

$N$  can be estimated by 
$$N = 2 * [t_{\alpha}(\gamma) + t_{\beta'}(\gamma)]^2 [\sigma / (\delta - 10)]^2$$

where

- $\sigma^2$  is the within subject variability
- $\gamma = N - 2$
- $\beta' = 1 - (1 - \beta)1/L$  where  $\beta$  is the Type II error and  $L$  the number of measurements
- $\alpha$  is the Type I error
- $t_{\alpha}(\gamma)$  the critical values for a Student T distribution with  $\gamma$  degrees of freedom at an  $\alpha$  level.
- $\delta$  is the expected difference between active drug and placebo (0 if no difference expected, >0 if drug is expected to slightly increase QT).

Considering an expected intra-variability of the primary endpoint of  $\sigma = 9$  ms and an expected difference of  $\delta = 2$  ms between P03277 (two doses) and placebo, 40 subjects are needed to demonstrate non-inferiority with a non-inferiority margin of 10 ms, a power of  $1 - \beta = 85\%$  and a Type I error of  $\alpha = 5\%$  one-sided on the  $L = 9$  measurements.

This sample size is also sufficient to detect a difference of 5 ms (with an expected difference of 12 ms for at least one timepoint and an expected intra-variability of the primary endpoint of  $\sigma = 9$  ms) of the primary endpoint between moxifloxacin and placebo with a power of 85%.

To account for potential dropouts and/or unevaluable data points, 48 subjects will be randomized in the trial. The recruitment could be stopped before 48 subjects from the time the number of fully evaluable subjects for the primary criterion is 40. That is to say having took part to the study, until the last scheduled ECG holter recording.

A dropout is a subject who is prematurely discontinuing the trial before the end of the last holter ECG recording.

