CONFIDENTIAL	
STATISTICAL ANALYSIS PLAN N° GDX-44-006
 
VERSION N° 2.0      DATED: 24JUL2018
 
██████████
	
██████████
 
Page 23 / 57

--------------	--	---

	Blood sample results for long term elimination missing	PK database	Non major
	Blood sample for plasma concentration not performed	Clinical database	Non major
	Results for plasma concentration missing	PK database	Non major
	Tolerance at injection site not performed	Clinical database	Non major
	VAS questionnaire not completed while subject reported pain	Clinical database	Non major
	Visit not done	Clinical database	Non major
Non respect of study's schedule and procedures	Urine sample for drug screening not performed at latest the day before first administration	Clinical database	Non major
	Blood samples collection for P03277 plasma concentration assessment not performed after vital signs	Clinical database	Non major
	Blood samples collection for laboratory data not performed before IMP /AMP administration of first period	Clinical database	Non major
	Vitals signs not performed at scheduled time	Clinical database	Non major
	Blood samples collection for P03277 plasma concentration not performed at scheduled timepoint	Clinical database	Non major
	12-lead Holter ECG not performed at scheduled time	ECG database	Non major
	12-lead safety ECG not performed at scheduled time	ECG database	Non major
	Initiation of Holter not performed 1 hour before administration	Clinical database	Non major
	12-lead Holter ECG not performed according to procedures	Monitoring	Non major
	12-lead safety ECG not performed according to procedures	Monitoring	Non major
	Blood sample collection not performed at scheduled time	Clinical database	Non major
	Not allowed retest	Monitoring	Non major
	VAS questionnaire not correctly printed	Monitoring	Non major

Subjects presenting at least one major protocol deviation will be excluded from the Per Protocol Set.

CONFIDENTIAL	STATISTICAL ANALYSIS PLAN N° GDX-44-006  VERSION N° 2.0      DATED: 24JUL2018  	  Page 24 / 57
--------------	--	---

Frequency and percentages of subjects with protocol deviations will be presented by sequence group and overall breaking down by status (major/non major). A listing of all protocol deviations will also be provided in CSR appendix 16.2.2 and major protocol deviations will be flagged.

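### The optional stop at 40 counts Holter completers, while the primary analysis drops anyone with a major deviation, so it can run on fewer than the 40 subjects stated as needed

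*Protocol*

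**What the plan says.** Protocol 11.2 concludes that "40 subjects are needed to demonstrate non-inferiority with a non-inferiority margin of 10 ms" (85% power, one-sided 5%). It then plans to randomise 48, to cover both dropouts and data points that cannot be evaluated. The next sentence is the permission at issue: "The recruitment could be stopped before 48 subjects from the time the number of fully evaluable subjects for the primary criterion is 40". The meaning of fully evaluable follows at once and carries no condition about deviations. In the SAP's version (3.3): "That is to say having took part to the study, until the last scheduled ECG holter recording". The synopsis has the same rule.

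The primary analysis uses a different population. Protocol 11.3.2 defines the Per Protocol Set as the randomised subjects without a major deviation at any time in the trial, and says of it: "Primary analysis will be performed on this set". Protocol 11.3.6 and 11.4.6 and SAP 3.9 and 5.5.1.2 agree. SAP 5.2 makes one deviation enough: "Subjects presenting at least one major protocol deviation will be excluded from the Per Protocol Set". Protocol 11.3.3 and SAP 5.2 place the final major/non-major classification at the data review meeting, before the blind is broken.

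**The concern.** The number that opens the stop and the number that drives the primary analysis come from different populations, and nothing in either document connects them. A major deviation is by definition one that affects the primary criterion. A subject can therefore count as fully evaluable for that criterion and still be left out of its primary analysis because of a deviation that affects it.

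The randomisation target of 48 was set to absorb two kinds of loss, dropouts and unevaluable data. The stop rule checks only the first. If the sponsor closes recruitment at exactly 40 completers and some are later excluded, the primary analysis falls below the plan's own requirement at a time when replacement may no longer be possible. Success needs every timepoint at both doses to pass, so lost precision raises the chance that a drug without a relevant effect fails the test.

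**Working it through.** **1. Can a Holter completer be excluded?** SAP 5.2 classes these as major: administered volume more than 20% from the calculated volume; extravasation; a product other than the one allocated; medication during confinement that affects the primary criterion; a broken code; more than 3 baseline QTcF measurements missing. None of them prevents a subject from reaching the last Holter recording. Each subject has three intravenous injections and four baselines, so there are several occasions for such a deviation.

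**2. Inputs (Protocol 11.2).** σ = 9 ms, δ = 2 ms, margin 10 ms, α = 5% one-sided, power 85%, L = 9 measurements, degrees of freedom N − 2. SAP section 4 raises the number of tested timepoints from 9 to 11; SAP 3.3 keeps L = 9.

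**3. The plan's figure.** N = 2[t_α(N−2) + t_β′(N−2)]² × [9/(2−10)]², with β′ = 1 − 0.85^(1/L).
- L = 9: β′ = 0.0179, N = 37.9, so 38. The stated 40 is within two subjects of this and is the next multiple of the four sequences.
- L = 11: β′ = 0.0147, N = 39.5, so 40.

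**4. Power at a given Per Protocol size n.** Inverting the same formula: power = [P(T_{n−2} < 8/(9√(2/n)) − t_{0.95, n−2})]^L.

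Example, n = 37: 8/(9√(2/37)) = 3.823; minus t = 1.690 gives 2.134; the probability is 0.9800; raised to the power 9 it is 0.834.

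| Subjects in Per Protocol Set | L = 9 | L = 11 |
|---|---|---|
| 40 | 88.2% | 85.8% |
| 39 | 86.8% | 84.1% |
| 38 | 85.2% | 82.2% |
| 37 | 83.4% | 80.1% |
| 36 | 81.4% | 77.8% |
| 34 | 76.9% | 72.6% |

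Starting from 40 completers, power drops below 85% at the third exclusion with 9 timepoints and at the first with 11.

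**5. How likely is a shortfall?** The documents give no rate of major deviations among completers, so q below is an assumption. If recruitment stops at exactly 40 completers, P(fewer than 40 remain) = 1 − (1−q)^40, and P(fewer than 38 remain) is the binomial chance of three or more exclusions.

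| Assumed q | Fewer than 40 | Fewer than 38 | Completers for an expected 40, 40/(1−q) |
|---|---|---|---|
| 1% | 33% | 0.7% | 41 |
| 2% | 55% | 4.6% | 41 |
| 5% | 87% | 32% | 43 |
| 10% | 98.5% | 78% | 45 |

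The last column stays within 48 throughout, provided that many subjects complete.

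**The case against.** The strongest reply is that the clause may seldom operate. It is a permission, not an instruction, and the base plan is to randomise 48. SAP 1.2 adds that volunteers are enrolled in cohorts of 8. Five cohorts make 40 and six make 48. If cohorts are always filled, stopping at 40 requires all of the first 40 to complete; the chance of that is 0.98^40 = 45%, 0.95^40 = 13% or 0.90^40 = 1.5% at assumed dropout rates of 2%, 5% and 10%. Otherwise a sixth cohort takes the total to 48, and changing the stop rule alters nothing. This argument largely stands, although only the SAP mentions cohorts and neither document rules out a partial sixth one.

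Other points also carry weight. With L = 9 the first two exclusions cost nothing against the 85% target, though the SAP's 11 timepoints remove that slack. Confinement, control of medication and the power injector should keep deviations few. Dropout is not itself listed as major, so a non-completer with partial data may remain in the Per Protocol Set and offset an exclusion; the offset is partial, since a Holter that was not performed is major. The formula treats timepoints as independent: positive correlation would raise power, while counting both doses would lower it.

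A reader might go further and infer that the trial will be underpowered, or that a conclusion of no QTc prolongation would become unreliable. The documents support neither. No deviation rate is given, and the intersection-union test keeps its one-sided 5% level whatever the number analysed. The repeat on the Full Analysis Set keeps the excluded completers, but it is supportive and does not replace the primary result.

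**Conclusion.** The mismatch is real and the same in the synopsis, Protocol 11.2 and SAP 3.3: the stop rule as worded does not secure the 40 subjects it is meant to secure. Its consequence is limited. It is a possible loss of power, from 88.2% at 40 to 83.4% at 37 with 9 timepoints, or from 85.8% at 40 to 84.1% at 39 with 11. It arises only if the sponsor uses the option at or very near 40 completers and deviations then remove some of them. The power figures rest on the plan's σ, δ and independence of timepoints, for one dose; the probabilities of a shortfall rest on assumed rates. The point merits a correction because that correction is cheap, not because the trial's conclusion is in doubt.

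**What to change.** In the synopsis, Protocol 11.2 and SAP 3.3, allow recruitment to stop before 48 only when 40 subjects have completed the last Holter recording and have no SAP 5.2 major deviation identified so far, with the baseline ECGs confirmed by the core laboratory. Otherwise continue to the planned maximum of 48.

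Make the count blinded. Product-allocation errors are traced through the randomisation database, so they should be counted by the unblinded third party who prepares and gives the injections (Protocol 5.3.3), and that person should report only a number.

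The cost is a change of wording in three places, one additional deviation count before recruitment closes, and at most the 8 subjects already in the plan. Per Protocol status can still change at the data review meeting, so the rule lowers the risk of a shortfall but cannot guarantee 40.
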